- DSMB report will be submitted to NIH within one week after each quarterly scheduled meeting. However, any action by the DSMB resulting in a temporary or permanent suspension of the clinical study will be reported to the NIH Program Official responsible for the grant within 48 hours. Any death will requires expedited reporting to NIH program officer within 24 hours of study's knowledge of death.

Reportable Adverse Events, including Serious Events

Definitions

Adverse Event (AE), also referred to as an adverse experience, is any untoward medical occurrence in humans, whether or not considered intervention related, which occurs during the conduct of a clinical trial. Any change in clinical status, routine labs, x-rays, physical examinations, etc., that is considered clinically significant by the study investigator is considered an AE. Adverse events will include: hypothermia (defined as temp less than 35.5 degree C), abnormal changes in vital signs including respiratory rate (apnic episodes or respiratory rate more than 70/min), heart rate (less than 70/min or more than 220/min), and oxygen saturation (less than 85%), . The staff nurses normally records any abnormal vital signs findings as part of their routine NICU care for all babies. These data will continuously be recorded during the cold feeding (usually around 15 minutes). Changes in vital signs can be a routine and frequent occurrences in preterm babies as part of their pathophysiology, The following AEs if occurred during the cold feeding will result in study termination for that baby and notification of the DSMB committee:

- 1- Any incidence of hypothermia
- 2- More than 2 episodes of apnea
- 3- Tachypnea defined as increase respiratory rate more than 70/min for more than 2 minutes
- 4- More than 2 episodes of bradycardia (defined as HR less than 70 for more than 10 seconds).
- 5- Tachycardia (defined as HR more than 220) for more than one minute

6- More than 2 episodes of desaturation (defined as O2 saturation less than 85%) for more than 30 seconds

Serious Adverse Events (SAEs), as determined by the PI, are any event that results in any of the following outcomes:

- 1. Death
- 2. Life-threatening SAE (life-threatening means that the study participant was, in the opinion of the investigator, at immediate risk of death from the reaction as it occurred)
- 3. Inpatient hospitalization or prolongation of existing hospitalization

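### In the list that ends an infant's participation, apnea, bradycardia and desaturation trigger on a third episode, while tachypnea and tachycardia trigger on the length of one, so a single unresolved episode of the first three does not meet the list

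*Combined protocol and SAP*

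**What the plan says.** The list is in the combined protocol and SAP, under Reportable Adverse Events, including Serious Events, Definitions. The events on it, "if occurred during the cold feeding will result in study termination for that baby and notification of the DSMB committee". On monitoring, the same paragraph says: "These data will continuously be recorded during the cold feeding (usually around 15 minutes".

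The six items take three forms:

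- **Any occurrence.** Item 1: "Any incidence of hypothermia".
- **Length of one event.** Item 3: "Tachypnea defined as increase respiratory rate more than 70/min for more than 2 minutes". Item 5: "Tachycardia (defined as HR more than 220) for more than one minute".
- **Number of episodes.** Item 2: "More than 2 episodes of apnea". Item 4: "More than 2 episodes of bradycardia (defined as HR less than 70 for more than 10 seconds". Item 6: "More than 2 episodes of desaturation (defined as O2 saturation less than 85%) for more than 30 seconds".

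Item 2 gives no duration. Items 4 and 6 give a minimum duration but do not say when one episode is long enough by itself. No other section adds a duration trigger for these three signs.

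**The concern.** For tachypnea and tachycardia, the longer the abnormality lasts, the surer the rule is to be met. For apnea, bradycardia and desaturation, only a new episode moves the infant closer to the rule, and a new episode requires recovery first. An infant who does not recover stays at one episode. Within a single list, length therefore counts for two signs and, beyond a qualifying minimum, counts for nothing in three others.

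What is at stake is the automatic part of the safety rule. This is the only place where the protocol sets explicit vital-sign criteria that end an infant's participation and notify the DSMB of that infant. If the literal wording leaves out the unresolved event, that decision passes to the investigator's discretion, which an explicit list is meant to limit. Two sites or two investigators reading the list differently is not the issue here; a single faithful reading already gives the odd result.

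**Working it through.** The plan states no figure on this point, so there is none to reproduce. The check applies each item literally to simple records.

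**Inputs from the list**

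- Observation window: about 15 minutes, 15 × 60 = 900 s.
- Apnea: met if the number of episodes is > 2. The item gives no minimum length, so any event recorded as apnea counts.
- Bradycardia: met if the number of episodes longer than 10 s is > 2.
- Desaturation, reading A: met if the number of episodes longer than 30 s is > 2. Reading B, which the placing of the 30 s also allows: met if there are > 2 episodes and their total time is > 30 s.
- Tachypnea: met if any one event is > 120 s.
- Tachycardia: met if any one event is > 60 s.

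**Assumed records.** The episode lengths are chosen to sit just above the stated minimums or to fill the feed. They are not taken from data.

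| Sign | One of 900 s | Two of 450 s | Three of 11 s | Three of 31 s | One of 61 s | One of 121 s |
|---|---|---|---|---|---|---|
| Apnea | no | no | yes | yes | no | no |
| Bradycardia | no | no | yes | yes | no | no |
| Desaturation, reading A | no | no | no | yes | no | no |
| Desaturation, reading B | no | no | yes | yes | no | no |
| Tachypnea | yes | yes | no | no | no | yes |
| Tachycardia | yes | yes | no | no | yes | yes |

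**Results**

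1. One episode filling the feed scores 1. Since 1 is not > 2, apnea, bradycardia and desaturation do not meet the list. Two episodes of 450 s score 2 and do not meet it either.
2. Three bradycardias of 11 s meet it with 3 × 11 = 33 s of abnormal time. Three desaturations of 31 s meet it with 3 × 31 = 93 s.
3. One tachycardia of 61 s or one tachypnea of 121 s meets it.
4. The single-episode result for desaturation is the same under readings A and B, so the loose wording of item 6 does not affect it. Nor does it depend on the feed lasting exactly 900 s, because one episode scores 1 whatever its length.

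**Other routes, set beside the list**

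- *AE definition (same section).* Apneic episodes, heart rate below 70/min and saturation below 85% are AEs, with no count or duration attached. One such event is therefore an AE.
- *DSMB Responsibilities.* All AEs are presented with the interim analysis. The board meets quarterly and after each 10 enrolments.
- *Assessment of Severity.* The PI reviews every AE for seriousness, severity and causality, and the results go to the DSMB.
- *SAE definition and Study Halting/Termination.* An event that may jeopardize the infant's health can be an SAE, as the PI determines. An SAE stops the whole study.
- *Study Design and Principal Investigator Responsibilities.* A neonatologist attends the procedures, but no stopping criterion is attached to that presence.

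Each of these routes either reports the event or leaves the stop to judgement. None makes termination for that infant automatic.

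**The case against.** The strongest reply is that the gap has little practical effect. A neonatologist is at the bedside and would hardly leave an unresolved desaturation alone. The event is an AE whatever its length, all AEs go to the DSMB, and a serious one would stop the whole study, which is a stronger action than ending one infant's participation. The section also explains that vital-sign changes are common in preterm infants, which is a reason to tolerate isolated events. Different forms of trigger for different signs are not in themselves a contradiction.

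Most of this stands, and it limits what can be concluded. A reader might infer that the DSMB's count of adverse events is too low, or that the halting decision for frequent AEs is biased. The documents do not support that: halting rests on AEs, not on list triggers, and a single prolonged event is already an AE. A reader might also infer that an infant with an unresolved event would go on to the other cold exposure. The list would not prevent it, but the SAE route and the attending neonatologist might, so continuation is not shown.

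What the reply does not do is explain the wording. Tolerance of brief, isolated changes is a reason not to act on a first short episode. It gives no reason why an episode that does not end should count for less than three that do, when the same list uses length for two other signs.

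**Conclusion.** The point holds as an inconsistency within the list. Taken literally, one apnea, bradycardia or desaturation of any length during the cold feed does not meet the criteria, while 33 s of bradycardia or 93 s of desaturation split into three episodes does. The consequence is limited to the automatic per-infant termination and the DSMB notification tied to it, which for such an event would rest on judgement.

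The conclusion assumes that an unbroken event is one episode, which is the ordinary meaning; the protocol does not define the term. The records in the working test the wording and do not estimate impact. A ratio of abnormal times formed from them would reflect only the lengths chosen, and the documents give no frequency for prolonged events. No planned efficacy or equivalence analysis uses the list. It is worth correcting because a written safety rule should not give a perverse result when it is followed exactly.

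**What to change.** **Protocol wording.** The sponsor, the study neonatologists and the DSMB should reconcile items 2, 4 and 6 with items 3 and 5 and state how a single prolonged episode is handled. They should also make clear whether the 30 s in item 6 applies to each episode or to the total. Which limits apply, and whether each sign needs a count, a length or both, are clinical decisions for them; none is proposed here.

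**Reporting.** Record the duration of each episode from the recording made during the cold feed, as far as it allows. Report to the DSMB, per infant and per cold feed, the number of episodes, the longest episode and the total time beyond each threshold.

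**Cost.** A short wording change and a few derived variables. The protocol calls the recording continuous, but that sentence follows one about nurses noting abnormal findings, so whether durations can be extracted should be confirmed first. Depending on how the items are reconciled, a few more infants may meet the rule.
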